# 4. Study Design

# 4.1. Summary of Study Design

Study J2T-MC-KGBO (KGBO) is an open-label, phase 3b study, which is 24 weeks in treatment duration. The study is designed to evaluate the safety and efficacy of lebrikizumab in male and female adult and adolescent participants with moderate-to-severe AD who have been previously treated with dupilumab.

#### **Study Periods**

This trial has 4 study periods:

- Screening (Visit 1:  $\leq$ 30 days prior to baseline)
- Treatment (Visits 2-9: 24 weeks)
- Safety follow-up (Visit 801: at Week 34 or approximately 12 weeks after last treatment)
- Continued Access (Visits 501, 502, and 503)

Participants who enroll into KGBO Protocol Addendum 2 will move directly into the Continued Access Period after completing the 24-week treatment period. Such participants will not complete Visit 801. A post-treatment follow-up visit (V901) will occur approximately 12 weeks post the last dose at the end of the Continued Access Period for the participants who do not move to commercial lebrikizumab or who discontinued early from the Continued Access Period. Please refer to KGBO Protocol Addendum 2 for more information.

#### Visit Types

Study visits at Week 12 (Visit 6) and Week 20 (Visit 8) will be performed virtually, that is, via telephone or telemedicine tools.

All other visits will be conducted at the clinical trial site.

#### Dosing

During the 24-week Treatment Period, approximately 120 participants will receive treatment:

- 500 mg subcutaneous (SC) loading dose at baseline and Week 2, followed by 250 mg SC Q2W until Week 16.
- Responders, defined as achieving IGA(0,1) or EASI-75 at Week 16, will receive Q4W dosing and will administer study intervention at Week 20.
- Inadequate responders at Week 16 will receive Q2W dosing and will administer study intervention at Weeks 18, 20, and 22.

During the Continued Access Period, eligible participants will continue lebrikizumab on the same dosing regimen (Q2W or Q4W) they were assigned at Week 16. Please refer to KGBO Protocol Addendum 2 for more information.

[figure not shown]
The study population is described in Section 5.1.1.

The efficacy and safety assessments are described in Sections 5.11 and 5.13 respectively.

## 4.1.1 Number of Participants

Approximately 120 participants previously treated with dupilumab will be enrolled to study intervention. Among those, approximately 80 participants will be enrolled who discontinued dupilumab due to: a) no response to treatment, b) a partial response to treatment, or c) who lost response to treatment. Additionally, approximately 15 participants will be enrolled who discontinued dupilumab treatment due to intolerance or adverse events (AEs). Finally, approximately 25 participants will be enrolled who stopped dupilumab treatment for other reasons (for example, cost, insurance coverage, access to medication, previous trial participants).

Approximately 10% (n=12) of participants will be adolescents ( $\geq$ 12 to <18 years, weighing  $\geq$ 40 kg). Patients will be evaluated for study eligibility before the baseline visit (Day 1).

# 4.1.2 Schema

Figure KGBO.4.1

Abbreviations: EASI = Eczema Area and Severity Index; IGA = Investigator's Global Assessment; n = number; Q2W = once every 2 weeks; Q4W = once every 4 weeks; SC = subcutaneous; W = week.

a Weeks 12 and 20 are phone visits.

b 30-day screening window.

c Lebrikizumab loading dose of 500 mg SC will be administered at baseline and Week 2.

dResponders: Participants who reach IGA 0 or 1 (clear or almost clear) or a 75% reduction in the EASI score from baseline (EASI-75). Inadequate responders are participants who do not reach these criteria.

e The safety follow-up visit will occur approximately 12 weeks after last study intervention injection.

fThe planned maximum duration of Continued Access treatment will vary for each participant enrolled into KGBO Protocol Addendum 2 and will end if and when the participant meets criteria for discontinuation of study intervention or discontinuation from the study. Participants may remain in the Continued Access Period as long as these criteria for discontinuation are not met and until the sponsor stops the study and addendum.

g Participants in the Continued Access Period will receive the same dose they were taking during Weeks 16 to 24 of the Treatment Period.

#### 4.2. Determination of Sample Size

Based on available data, the anticipated EASI-75 response rate is approximately 50%. A total sample size of 120 enrolled participants will provide >95% probability that the half-width of the 2-sided 90% CI of the EASI-75 response rate is at most 10%.

Example point estimates for EASI-75 response rates and corresponding 2-sided 90% CIs based on the Wilson-Score method for a sample size of 120 participants are summarized in the table below. The CIs are provided as reference rather than a basis of any decision criteria.

Example Point Estimates	Lower Bound of 90% CI	Upper Bound of 90% CI
40%	32.9%	47.5%
45%	37.7%	52.5%
50%	42.6%	57.4%
55%	47.5%	62.3%
60%	52.5%	67.1%

Table KGBO.4.1 Estimated 90% CI with Sample Size of 120 Participants

#### 4.3. Method of Assignment to Treatment

This is an open-label study. All enrolled patients will be assigned to 250-mg lebrikizumab Q2W at the baseline visit. At Week 16, patients will be assigned to 250-mg lebrikizumab Q2W or 250-mg lebrikizumab Q4W based on their IGA or EASI score.

# **5.A Priori Statistical Methods**

### 5.1. General Considerations

Statistical analysis of this study will be the responsibility of ICON. The latest version of the MedDRA will be used.

Summaries from assessment of endpoints described in the protocol are planned to be included in a CSR. Summaries for key safety data are also planned to be included in the CSR. Results from additional efficacy summaries and other safety summaries may also be provided in the CSR as deemed appropriate.

Any change to the data analysis methods described in the protocol will require a protocol amendment ONLY if it changes a principal feature of the protocol. Any other change to the data analysis methods described in the protocol and the justification for making the change will be described in the CSR.

All statistical processing will be performed using SAS® 9.4 unless otherwise stated.

The schedule of visits and procedures outlined in the protocol specifies the allowable windows for assessments. Assessments performed outside these windows will not be excluded from any summaries, unless specified otherwise.

#### 5.1.1. Analysis Populations

Analysis populations are defined in Table KGBO.5.1 along with the analyses they will be used to conduct. The number of patients included in each population will be summarized.

Population	Description	
All Entered Patients	All patients who signed informed consent. Patient flow will be summarized.	
Intent-to-Treat (ITT)	All enrolled patients according to their planned intervention. Unless otherwise	
Population	specified, efficacy and health outcomes analyses for Weeks 0 to 16 of the	
	Treatment Period will be conducted on this population.	
Safety Population	All enrolled patients who received at least 1 confirmed dose of lebrikizumab	
	250 mg. Safety analyses will be conducted on this population.	
Treatment Period II	All enrolled patients who received at least 1 confirmed dose of lebrikizumab	
Population	250 mg during Weeks 16 to 24 of the Treatment Period. Unless otherwise	
	specified, efficacy and health outcomes analyses for Weeks 16 to 24 of the	
	Treatment Period will be conducted on this population. Additional efficacy	
	analyses for Weeks 0 to 24 of the Treatment Period may also be conducted on	
	this population.	

Table KGBO.5.1. Analysis Populations

# 5.1.2. General Considerations for Analyses

All analyses will be descriptive. Frequencies, percentages, and 90% Wilson-Score CIs for percentages will be reported for discrete efficacy endpoints. Mean, standard deviation, minimum, Q1, median, Q3, maximum, and the number of participants will be reported for continuous

efficacy endpoints. AEs, discontinuation, and other categorical safety data will be summarized using frequencies and percentages. Continuous vital signs, body weight, and other continuous safety variables including laboratory variables will be summarized descriptively as well.

#### Baseline

Baseline will be defined as the last available value before the first injection for efficacy and health outcome analyses. In most cases, this will be the measure recorded at the baseline visit (Day 1). If the patient does not take any injection, the last available value on or prior to treatment assignment date will be used. Change from baseline will be calculated as the visit value of interest minus the baseline value.

For Pruritus Numeric Rating Scale (NRS), Skin Pain NRS, and Sleep-Loss due to Pruritus collected via eDiary, the baseline period is the 7-day window prior to the first injection. A patient must have responses on at least 4 of 7 days to calculate a baseline weekly mean. If a patient has 3 or fewer responses, the baseline mean value will be considered missing.

For the safety analyses, the following baselines will be used. For safety analyses using a baseline period, the baseline period is defined as the time from the screening visit to the date/time of the first injection.

- TEAEs: baseline will be all results recorded during the baseline period.
- Treatment-emergent abnormal laboratory and vital signs results: baseline will be all results recorded during the baseline period.
- Change from baseline to last post-baseline observation or to each scheduled postbaseline visit for laboratory and vital signs results: baseline will be the last scheduled non-missing assessment recorded during the baseline period.

## 5.2. Primary and Supportive Estimands

There will be five estimands addressing different clinical questions of interest and intercurrent events for the primary and secondary endpoints.

## 5.2.1. Primary Estimand for the Primary Endpoint

The primary estimand for the primary endpoint represents the primary clinical question of interest: What is the intervention effect in percentage of participants achieving at least 75% improvement from baseline in Eczema Area and Severity Index (EASI) after 16 weeks of lebrikizumab 250 mg Q2W intervention in participants with moderate-to-severe AD who have been previously treated with dupilumab and who remain on study treatment until Week 16?

The primary estimand for the primary endpoint is described by the following attributes:

- A. Population: participants with moderate-to-severe AD who have been previously treated with dupilumab and who remain on study treatment until Week 16.
- B. Endpoint: whether participants achieve at least 75% improvement from baseline in EASI at Week 16.

- C. Intercurrent events: There are no intercurrent events for this population since participants who initiate rescue medication are discontinued from the study and hence study treatment. Therefore, participants who stay on study treatment through Week 16 will not have an intercurrent event such as initiating rescue medication or permanently discontinuing treatment.
- D. Population-level summary: percentage of participants achieving EASI-75 response at Week 16.

#### 5.2.2. Supportive Estimands for the Primary Endpoint

There are two supportive estimands for the primary endpoint. The first is a hybrid estimand representing the following clinical question of interest: What is the intervention effect in percentage of participants achieving at least 75% improvement from baseline in Eczema Area and Severity Index (EASI) after 16 weeks of lebrikizumab 250 mg Q2W intervention in participants with moderate-to-severe AD who have been previously treated with dupilumab if all participants adhered to treatment except those who discontinued due to lack of efficacy?

This estimand is described by the following attributes:

- A. Population: participants with moderate-to-severe AD who have been previously treated with dupilumab.
- B. Endpoint: whether participants achieve at least 75% improvement from baseline in EASI at Week 16.
- C. Intercurrent events (ICEs): One ICE, permanent treatment discontinuation, is considered by this estimand as follows:
  - a. Participants who discontinue treatment due to lack of efficacy prior to Week 16 will be considered as treatment failures, i.e. non-responders, after the ICE. Therefore, a composite strategy is used for this type of ICE.
  - b. For participants who discontinue treatment due to reasons other than lack of efficacy prior to Week 16, a hypothetical strategy will be used to estimate what the treatment effect would have been if subjects continued with treatment. Therefore, a hypothetical strategy is used for this type of ICE.
- D. Population-level summary: percentage of participants achieving EASI-75 response at Week 16.

The second supportive estimand for the primary endpoint is a hypothetical estimand representing the following clinical question of interest: What is the intervention effect in percentage of participants achieving at least 75% improvement from baseline in Eczema Area and Severity Index (EASI) after 16 weeks of lebrikizumab 250 mg Q2W intervention in participants with moderate-to-severe AD who have been previously treated with dupilumab if all participants adhered to treatment?

This estimand is described by the following attributes:

A. Population: participants with moderate-to-severe AD who have been previously treated with dupilumab.

- B. Endpoint: whether participants achieve at least 75% improvement from baseline in EASI at Week 16.
- C. Intercurrent events (ICEs): One ICE, permanent treatment discontinuation, is considered by this estimand as follows:
  - a. For participants who discontinue treatment prior to Week 16, a hypothetical strategy will be used to estimate what the treatment effect would have been if all subjects continued with treatment. Therefore, a hypothetical strategy is used for this type of ICE.
- D. Population-level summary: percentage of participants achieving EASI-75 response at Week 16.

## 5.2.3. Estimands for Secondary Endpoints at Week 16

The primary estimand for the primary endpoint will be applied to all secondary endpoints at Week 16. The supportive estimands for the primary endpoint will also be applied to all secondary endpoints at Week 16.

## 5.2.4. Estimands for Secondary Endpoints at Week 24

The primary estimand for the primary endpoint will be applied to all secondary endpoints at Week 24. There are two supportive estimands for secondary endpoints at Week 24. The first is a hybrid estimand representing the following clinical question of interest: What is the intervention effect in successful responses or means after 24 weeks of lebrikizumab intervention in participants with moderate-to-severe AD who have been previously treated with dupilumab if all participants adhered to treatment except those who discontinued due to lack of efficacy?

This estimand is described by the following attributes:

- A. Population: Treatment Period II population as described in Section 5.1.1.
- B. Endpoint: apply to all secondary endpoints at Week 24.
- C. Intercurrent events (ICEs): One ICE, permanent treatment discontinuation, is considered by this estimand as follows:
  - a. Participants who discontinue treatment due to lack of efficacy after Week 16 will be considered as treatment failures, i.e. non-responders, after the ICE. Therefore, a composite strategy is used for this type of ICE.
  - b. For participants who discontinue treatment due to reasons other than lack of efficacy after Week 16, a hypothetical strategy will be used to estimate what the treatment effect would have been if subjects continued with treatment. Therefore, a hypothetical strategy is used for this type of ICE.
- D. Population-level summary: percentage of successful responses or means at Week 24.

The second supportive estimand for secondary endpoints at Week 24 is a hypothetical estimand representing the following clinical question of interest: What is the intervention effect in successful responses or means after 24 weeks of lebrikizumab 250 mg Q2W intervention in

participants with moderate-to-severe AD who have been previously treated with dupilumab if all participants adhered to treatment?

This estimand is described by the following attributes:

- A. Population: Treatment Period II population as described in Section 5.1.1.
- B. Endpoint: apply to all secondary endpoints at Week 24.
- C. Intercurrent events (ICEs): One ICE, permanent treatment discontinuation, is considered by this estimand as follows:
  - a. For participants who discontinue treatment after Week 16, a hypothetical strategy will be used to estimate what the treatment effect would have been if all subjects continued with treatment. Therefore, a hypothetical strategy is used for this type of ICE.
- D. Population-level summary: Population-level summary: percentage of successful responses or means at Week 24.

Because participants who initiate rescue medication are required to discontinue from the study and hence permanently discontinue study treatment, the supportive estimands for the primary and secondary endpoints only consider permanent treatment discontinuation as an ICE.

Analytical details on how missing data including those as a result of intercurrent events will be handled can be found in Section 5.4. The following table (Table KGBO.5.2) summarizes the analytical strategies that will be conducted on the intercurrent events for the five estimands.

		Analysis Stra Perman Disco	Missing Data		
Estimand	Population	Due to lack of efficacy	Due to any other reasons, including initiation of rescue medication	Imputation Method	
Primary Estimand for the Primary Endpoint and Secondary Endpoints	ITT Population who remained on treatment	Not applicable	Not applicable	Primary analysis: as observed	
Supportive Estimand for the Primary Endpoint and Secondary	ITT Population	Composite: Set to baseline	Hypothetical: Set to missing	MCMC-MI	

Endpoints at Week 16 (Hybrid)				
Supportive Estimand for the Primary Endpoint and Secondary Endpoints at Week 16 (Hypothetical)	ITT Population	Hypothetical: Set to missing	Hypothetical: Set to missing	LOCF
Supportive Estimand for Secondary Endpoints at Week 24 (Hybrid)	Treatment Period II Population	Composite: Set to baseline	Hypothetical: Set to missing	MCMC-MI
Supportive Estimand for Secondary Endpoints at Week 24 (Hypothetical)	Treatment Period II Population	Hypothetical: Set to missing	Hypothetical: Set to missing	LOCF

Abbreviations: ICE = intercurrent event; LOCF = last observation carried forward; MCMC = Markov chain Monte Carlo; MI = Multiple Imputation.

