4.2. Scientific Rationale for Study Design

The top-line results from 2 randomized controlled monotherapy phase 3 studies of lebrikizumab (ADvocate 1 and ADvocate 2) and a third completed phase 3 trial of lebrikizumab in combination with topical steroids (ADhere) demonstrated positive risk benefit in adult and adolescent patients with moderate-to-severe AD at Week 16. The safety profile of these 3 studies was consistent with prior AD lebrikizumab studies and demonstrated favorable benefit: risk profile in moderate-to-severe AD patients. Additional detailed discussion of the lebrikizumab studies (preclinical and clinical) is provided in the lebrikizumab IB.

Since randomized controlled data is already available, this study will be conducted as an open label study to mimic the real-world patient experience. Week 16 data will be used as the primary endpoint in this study and the safety and efficacy until Week 24 will also be evaluated to understand the durability of effect post Week 16.

The open-label trial design is appropriate as no direct comparison of therapeutic treatments will be made. Rather, this study will determine the efficacy and safety of lebrikizumab treatment in a patient population that previously discontinued use of dupilumab, the first targeted therapy available for treatment of AD. The participants recruited into this study have taken dupilumab for treatment of moderate-to-severe AD; it is possible that many of these patients may have more difficult to treat AD and they may therefore need adjunct topical therapy to control their symptoms. To make the study closer to a real world-setting and also to avoid participant discomfort, use of mild/moderate potency topical steroids/topical calcineurin inhibitors (TCI)/topical phosphodiesterase-4 (PDE4) inhibitors will be allowed during the study.

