### 5.4.1. As Observed Analysis

The "as observed" strategy is used in so-called "observed cases" or "completers" analysis ubiquitous in the literature. For this analysis, only data from completers at the visit are relevant. All efficacy data will be summarized using an "as observed" analysis and summaries based on observed data at each postbaseline visit will be provided.

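### Week 24 endpoints inherit an estimand that is defined only to Week 16, so the main Week 24 summary can overstate durability

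*SAP*

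**What the plan says.** SAP 5.2.4 opens with the rule that "The primary estimand for the primary endpoint will be applied to all secondary endpoints at Week 24". It does not restate the attributes for the later time point, so they come from SAP 5.2.1. The population there is "participants with moderate-to-severe AD who have been previously treated with dupilumab and who remain on study treatment until Week 16". On intercurrent events, 5.2.1 says: "There are no intercurrent events for this population since participants who initiate rescue medication are discontinued from the study and hence study treatment". It concludes that "participants who stay on study treatment through Week 16 will not have an intercurrent event such as initiating rescue medication or permanently discontinuing treatment".

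Table KGBO.5.2 has one row for this estimand, covering the primary endpoint and the secondary endpoints. Its population is "ITT Population who remained on treatment", both intercurrent-event columns are marked not applicable, and the method is as observed. SAP 5.4.1 explains that for this method "only data from completers at the visit are relevant".

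SAP 5.2.4 also plans two supportive estimands at Week 24, both on the Treatment Period II Population and both treating permanent discontinuation after Week 16 as an intercurrent event. In the hybrid, "Participants who discontinue treatment due to lack of efficacy after Week 16 will be considered as treatment failures". Every other stop is set to missing and multiply imputed, and Table KGBO.5.2 places initiation of rescue in that group. The second supportive estimand uses LOCF.

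Protocol 4.2 gives the purpose of the later data: "the safety and efficacy until Week 24 will also be evaluated to understand the durability of effect post Week 16". Protocol 6.8.5 requires participants who receive rescue to leave the study.

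**The concern.** The argument for having no intercurrent events depends on the population being defined by staying on treatment up to the time of assessment. That works at Week 16. At Week 24 the same people can still stop or need rescue during the last eight weeks, and the supportive estimands in the same section accept that they can.

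This matters because the loss can be related to outcome. Rescue is for intolerable worsening, and starting it ends study participation. A Week 16 responder who moves to Q4W, loses response and is withdrawn for rescue has no scheduled Week 24 EASI. That participant drops out of the main Week 24 rate instead of counting as a failure. The summary meant to show whether the effect lasts therefore leaves out some of the participants in whom it did not, and the Week 16 and Week 24 rates rest on different denominators.

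**Working it through.** **1. The plan's own figure.** SAP 4.2 gives a Wilson 90% CI of 42.6% to 57.4% for 50% of 120. With z = 1.645, the half-width is 1.645 × √(0.25/120 + 1.645²/(4 × 120²)) / (1 + 1.645²/120) = 7.4 points, so the interval reproduces, as do the other four rows of that table. This figure concerns Week 16 precision and is not in dispute. It serves below as a yardstick.

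**2. Which population applies at Week 24?**
- SAP 5.2.1, carried over by 5.2.4: on treatment until Week 16. Read literally, this includes people who stop between Weeks 16 and 24, whom the as-observed method then leaves out.
- Table KGBO.5.2: the ITT Population who remained on treatment, with no time limit. If this means to Week 24, not applicable is consistent, but the population is then selected by what happened after Week 16.
- Table KGBO.5.1: for Weeks 16 to 24, unless otherwise specified, the Treatment Period II Population (at least one confirmed dose in that period).

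On either reading of the estimand, a participant withdrawn for rescue after Week 16 is absent from the main Week 24 rate.

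**3. Size of the effect.** Let N be the number entering Weeks 16 to 24, k the number who leave, x the responders among those who stay, and q the response rate the leavers would count at.
- As-observed rate: p = x/(N − k)
- Rate with everyone counted: p − (k/N)(p − q)
- Overstatement: (k/N)(p − q), which is p × k/N when all leavers are non-responders (q = 0)

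The documents give no discontinuation rate for Weeks 16 to 24, so the leaver shares are assumed. N = 120 is the planned enrolment, p is taken near 60%, and q = 0.

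| Leavers | As observed | Leavers as non-responders | Gap (points) |
|---|---|---|---|
| 2 (about 2%) | 71/118 = 60.2% | 71/120 = 59.2% | 1.0 |
| 6 (5%) | 68/114 = 59.6% | 68/120 = 56.7% | 3.0 |
| 12 (10%) | 65/108 = 60.2% | 65/120 = 54.2% | 6.0 |
| 18 (15%) | 61/102 = 59.8% | 61/120 = 50.8% | 9.0 |
| 24 (20%) | 58/96 = 60.4% | 58/120 = 48.3% | 12.1 |

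For as-observed rates of about 50% to 70%, the gap is 0.8 to 1.2 points at 2% leavers, 5.0 to 7.0 at 10% and 10.0 to 14.0 at 20%. Starting from N = 108 changes little.

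**4. What the hybrid recovers.** Take the 10% row (12 leavers) and assume that imputed leavers respond at the stayers' rate.
- All coded lack of efficacy: 65/120 = 54.2%, the full correction.
- Half so coded: (65 + 6 × 0.602)/120 = 57.2%.
- All coded rescue or other: (65 + 12 × 0.602)/120 = 60.2%, no correction.

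**5. What LOCF recovers.** Week 20 is a virtual visit, and the Schedule of Activities has no EASI between Weeks 16 and 24 except at early discontinuation. SAP 5.4.2 does not say how that assessment is assigned to a visit. Assume 60 Week 16 responders, of whom 12 lose response (true maintenance 48/60 = 80%).

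| Of the 12, number who leave | As observed | LOCF from the Week 16 value |
|---|---|---|
| 0 | 48/60 = 80.0% | 48/60 = 80% |
| 6 | 48/54 = 88.9% | 54/60 = 90% |
| 12 | 48/48 = 100% | 60/60 = 100% |

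LOCF avoids this only if the early-discontinuation EASI is the value carried forward.

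**The case against.** The strongest reply is that the SAP does not rely on the as-observed summary alone. The hybrid counts lack-of-efficacy stops after Week 16 as non-responders, LOCF keeps every leaver in the denominator, and SAP 5.11 reports both beside the as-observed results. SAP 5.7 tabulates discontinuation before Week 24 by reason, and SAP 5.10 reports rescue use in Weeks 16 to 24. All of this stands. A reader might infer that leavers disappear from every Week 24 result; they do not. What remains is that no planned analysis is specified to count rescue after Week 16 as non-response.

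A reader might also infer that durability is overstated as a matter of fact. The documents do not support that. The direction depends on leavers doing worse than stayers, and the size depends on attrition that is not stated and that Protocol 7.2 expects to be uncommon. Participants who lose response but stay on treatment are counted correctly.

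Nor does the Week 16 regimen change by itself produce a rising rate, since only responders change regimen. Suppose 108 are assessed at Week 16 with 54 responders (50.0%). If 5 responders lose response and leave, the as-observed rate is 49/103 = 47.6% against 49/108 = 45.4%, still a visible fall. An apparent rise needs inadequate responders to leave as well: with 10 of them gone, the rate is 49/93 = 52.7%.

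Finally, Protocol 9.3.3 specifies all observed data for secondary endpoints. Demoting that summary would depart from the protocol, and failing every stop whatever its reason would change the clinical question. Both points stand and shape the remedy.

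**Conclusion.** The concern holds as a defect of definition with a conditional bias. The Week 24 endpoints carry a no-intercurrent-events statement that is justified only through Week 16, three passages give different Week 24 populations, and the main summary omits participants who stop or are withdrawn for rescue after Week 16.

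If all leavers are non-responders and the as-observed rate is near 60%, the overstatement is about 1 point at 2% leavers, 3 at 5%, 6 at 10% and 12 at 20%. At 10% this is close to the 7.4-point half-width in step 1. With attrition of a few percent it is minor, and if leavers would respond as stayers do it is zero. The supportive analyses narrow the gap but do not close it, because rescue starters are imputed and LOCF may retain a Week 16 response. The listed endpoints also include no maintenance rate among Week 16 responders, which is the direct measure of durability. The endpoints are secondary and descriptive, so this should be corrected but does not threaten the primary result.

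**What to change.** In SAP 5.2.4 and Table KGBO.5.2:
- State a separate Week 24 estimand with one population, reconciling 5.2.1 and Tables KGBO.5.1 and KGBO.5.2.
- Name discontinuation and rescue after Week 16 as intercurrent events, in place of the not-applicable entries.
- Keep the as-observed summary that Protocol 9.3.3 requires.
- Add a Week 24 analysis of the binary endpoints on the Treatment Period II denominator, with stops for lack of efficacy or rescue counted as non-response. Stops for unrelated reasons can keep the hybrid's imputation.
- Report the proportion of all Week 16 responders in that population who still respond at Week 24, with none removed from the denominator.
- State how the early-discontinuation EASI is assigned to a visit and whether LOCF uses it.

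The cost is SAP wording and one or two more tables from data already collected; study conduct does not change. The Week 24 rates may look less favourable.

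### The Week 24 supportive questions cover everyone previously treated with dupilumab, but their analyses leave out patients who stopped for lack of efficacy before Week 16

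*SAP*

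**What the plan says.** **Week 16 hybrid (SAP 5.2.2, Table KGBO.5.2).** The population is ITT. "Participants who discontinue treatment due to lack of efficacy prior to Week 16 will be considered as treatment failures". Their values are set to baseline.

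**Week 24 hybrid (SAP 5.2.4).** The question concerns the effect "after 24 weeks of lebrikizumab intervention in participants with moderate-to-severe AD who have been previously treated with dupilumab", with no condition on reaching Week 16. Attribute A then names the "Treatment Period II population as described in Section 5.1.1". SAP 5.1.1 defines that set by at least one confirmed dose of lebrikizumab "250 mg during Weeks 16 to 24 of the Treatment Period". The failure rule covers later stops only: "Participants who discontinue treatment due to lack of efficacy after Week 16 will be considered as treatment failures, i.e. non-responders, after the ICE". The data rule in SAP 5.4.3 has the same limit.

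**Week 24 hypothetical (SAP 5.2.4).** The question is equally unconditional and the population is again Treatment Period II. It also names 24 weeks at 250 mg Q2W. The secondary objective in SAP Table KGBO.3.1 likewise names Q2W for Weeks 16 and 24. SAP 4.1, 4.3 and the column head of Table KGBO.5.3 describe Q2W or Q4W after Week 16, according to response. The secondary objective in protocol section 3 names no regimen.

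**As-observed analysis.** Table KGBO.5.2 gives its population as "ITT Population who remained on treatment", and SAP 5.4.1 restricts it to completers at the visit.

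**The concern.** Protocol 4.2 uses the data up to Week 24 to judge whether the effect lasts beyond Week 16, so readers will set the two weeks side by side. All 16 secondary endpoints (8 binary, 8 continuous) get a hybrid result at both weeks. For EASI-75 the Week 16 result is the primary endpoint.

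The two hybrids treat the same patient differently. Someone who gives up treatment for lack of efficacy at Week 8, say, is a failure at Week 16 and absent at Week 24. Both the stated question and the protocol's secondary objective include that patient. A change between the two hybrids may then reflect who is counted and not what happened to anyone's skin.

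**Working it through.** **Step 1. Is the early lack-of-efficacy stop counted in any planned Week 24 efficacy analysis?**

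- As-observed: no, because only completers at the visit contribute (SAP 5.4.1).
- Hybrid by multiple imputation: no. The patient has no dose in Weeks 16 to 24 and so is outside Treatment Period II. The patient is excluded by population, not set to missing.
- Hypothetical by LOCF: no, same population.
- Optional extra work: SAP 5.1.1 says that efficacy "analyses for Weeks 0 to 24 of the Treatment Period may also be conducted on" Treatment Period II, so again no.
- Disposition (SAP 5.7): yes. Stops before Week 24 are tabulated by reason on ITT, but this yields no Week 24 response rate.

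**Step 2. The plan's own precision figure.** SAP 4.2 gives a 90% Wilson interval of 42.6% to 57.4% for 50% of 120. With z = 1.645 and z² = 2.706:

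half-width = 1.645 × √(0.25/120 + 2.706/(4 × 120²)) / (1 + 2.706/120) = 0.074

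This is 7.4 points and reproduces the table. It concerns Week 16 and serves here only as a yardstick.

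**Step 3. Size of the mismatch.** N = 120 and the anticipated 50% rate come from SAP 4.2. Everything else is assumed, because the documents give no early-stop rate. Protocol 7.2 says only that discontinuation should be uncommon.

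- e = lack-of-efficacy stops before Week 16
- m = other early leavers, with imputed response r′
- r = hybrid response rate in Treatment Period II, taken as equal at both weeks

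Week 16 ITT hybrid = [r(120 − e − m) + r′m]/120

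Week 24 hybrid = r

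Gap = [r·e + (r − r′)m]/120, which is r·e/120 when r′ = r or m = 0.

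| e | Week 16 hybrid, r = 50% | Week 24 hybrid | Gap, r = 50% | Gap, r = 20% | Gap, r = 60% |
|---|---|---|---|---|---|
| 0 | 50.0% | 50.0% | 0 | 0 | 0 |
| 2 | 49.2% | 50.0% | 0.8 | 0.3 | 1.0 |
| 4 | 48.3% | 50.0% | 1.7 | 0.7 | 2.0 |
| 8 | 46.7% | 50.0% | 3.3 | 1.3 | 4.0 |
| 12 | 45.0% | 50.0% | 5.0 | 2.0 | 6.0 |

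Gaps are in percentage points (Week 24 minus Week 16). All lie below 7.4.

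**Step 4. Other early leavers.**

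- e = 8, m = 6, r = 0.5, r′ = 0.3: (4 + 1.2)/120 = 4.3 points, against 3.3 when r′ = 0.5.
- e = 2, m = 8, r = 0.5, r′ = 0.7: (1 − 1.6)/120 = −0.5 points. The direction reverses.

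**Step 5. Where the formula applies.** It needs the full denominator of 120. Five of the 16 endpoints have a baseline minimum: Pruritus 4-point, Pruritus 3-point, Sleep-Loss, Skin Pain and DLQI response. DLQI change and cDLQI change are limited by age (the DLQI response is too). So at least seven endpoints have smaller denominators. Diary endpoints may also lose patients with three or fewer baseline entries (SAP 5.1.2).

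**The case against.** The strongest reply is that the population is not hidden. Attribute A, Table KGBO.5.2 and SAP 5.1.1 all name Treatment Period II, and the SAP revision history says why it was added. It is a sensible set for durability. The optional Weeks 0 to 24 analyses on that set could give a like-for-like comparison of the two weeks. All of this stands, and the fix keeps Treatment Period II.

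A reader might infer a protocol departure, because protocol 9.2 defines only the ITT and Safety populations and 9.3.3 names the intent-to-treat set for threshold endpoints. The documents do not support that. Protocol section 3 lets the SAP add estimands, 9.3.3 describes the analysis of observed data, and the SAP keeps that analysis on ITT.

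A reader might also infer that the Week 24 hybrid must be inflated, on every endpoint, by the fraction e/120. Steps 4 and 5 show otherwise.

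The number e may also be small. Table KGBO.5.2 places rescue starters under "Due to any other reasons, including initiation of rescue medication", and inadequate responders at Week 16 continue treatment. This limits the size. It does not reconcile the question with its population.

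Finally, an ITT Week 24 hybrid must impute outcomes for people who never entered that period. That is a real cost, and it is why the analysis should be supportive only.

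**Conclusion.** The point holds as a mismatch between question and analysis. Both Week 24 supportive questions are unconditional and both analyses are conditional on dosing after Week 16. The two hybrids are not comparable, and no planned Week 24 efficacy analysis counts lack-of-efficacy stops before Week 16.

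The size is unknown. For full-denominator rates, with other early leavers responding like the rest, it is about 0.8 to 5.0 points at r = 50% for e = 2 to 12, and nothing at e = 0. The net direction is not certain.

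The Week 16 primary endpoint, the as-observed results and the sample size are untouched, and everything is descriptive. The correction should be made, but nothing central depends on it.

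Separately, the Q2W wording of the Week 24 hypothetical question and of the SAP secondary objective contradicts the response-based assignment at Week 16. No view is taken on which regimen is right.

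**What to change.** 1. Reword both Week 24 supportive questions as conditional on entering Weeks 16 to 24, and keep Treatment Period II as the durability summary.
2. Add one supportive, descriptive Week 24 hybrid on ITT. Set lack-of-efficacy stops at any time before Week 24 to baseline and treat rescue as Table KGBO.5.2 does. State an imputation rule for other early leavers: SAP 5.4.3 imputes within regimen group, and they have none. One option is to impute Week 16 first, then Week 24 within the group that this implies.
3. Reconcile the regimen wording in SAP Table KGBO.3.1 and 5.2.4 with SAP 4.1, 4.3 and Table KGBO.5.3.
4. Editorial only: label the Week 24 as-observed population as remaining on treatment until Week 24. No number changes.

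The cost is text edits, one extra analysis and one imputation rule, with no new data or visits. The added Week 24 rates will probably be slightly lower than those in Treatment Period II, though not certainly. The added rate is below r only if the other early leavers' imputed Week 24 response is below r(e + m)/m. At r = 50% and m = 8 that threshold is 0.5 × 10/8 = 62.5% for e = 2 and 0.5 × 12/8 = 75% for e = 4.
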